The primary endpoint is to assess the effects of HFNC on maintaining ventilation and oxygenation. This will be ascertained through the need for airway manipulations such as chin lift and jaw thrust to the placement of airway adjuncts such as oral or nasal airways.

In addition, the need for an increased FiO₂ will be recorded. Secondary endpoints will include the lowest and mean pulse oximetry readings, TcCO₂, TcO₂, and the change in these values from the beginning to the end of the procedure. Additional end points will record interruption or aborting of the procedure secondary to difficulties managing the patient's airway. Both groups will be placed on supplemental oxygen via nasal cannula and transported to the recovery room for observation prior to discharge. Pulse oximetry readings will be followed for an hour every 15 minutes after the completion of the procedure in the recovery room to assess for desaturation. Participants will also be evaluated on how they feel prior to discharge.

MATERIALS AND METHODS:

STUDY POPULATION

Participants are eligible for the study if they are greater than 18 years of age and are scheduled for an elective ambulatory upper and/or lower endoscopy under sedation in the gastrointestinal suite at the Moses Campus of the Montefiore

Medical Center. Participants must have a BMI greater than or equal to 40 kg/m².

Inclusion in the study will be voluntary without monetary compensation.

Participants will be excluded if they are less than 18 years of age, pregnant, have severe respiratory failure (hypercapneic and/or hypoxemic), use home oxygen at baseline, have a tracheostomy, or the procedure is an emergency. Patient selection will be obtained by reviewing the GI suite schedule a few days ahead of time screening for patient with a BMI greater than 40.

The patient's chart will then be reviewed during the normal anesthesia pre-operative assessment for criteria that would exclude the patient from the study. If no exclusion criteria are found, the patient will be contacted by phone and the study will be explained and the patient verbally consented. On the day of the procedure or if possible prior to the procedure the patient will sign written consent. The patients will be consented by a member of the study team.

STUDY DESIGN

Eligible patients will be randomized into two groups of thirty patients each¹¹,

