This is a pilot study, so a small number of patients per group was initially chosen. The number of patients in each group is based on our clinical observation while caring for patients in the endoscopy suite. The analysis of the outcome data, the proportion of patients requiring additional airway support, will be analyzed utilizing chi-square analysis. Current clinical practice at our hospital varies, the use of HFNC is a physician preference. Even though it is considered as a standard of care, not all Anesthesiologists are experienced using it. If the Anesthesiologist assigned to the case is not familiar with or not comfortable with HFNC, the patient will be excluded from the study. Although MAC sedation utilizing a nasal cannula for oxygenation is routinely performed, a significant number of morbidly obese patients are electively intubated and placed under general anesthesia for these endoscopic procedures. Patients that are endotracheal intubated will be excluded from the study. The research portion of the study is randomly assigning the

patients into one of two groups, every thing else follows the standard of care at our hospital.

RANDOMIZATION

This is a randomized controlled study. Anesthesia research office that is not part of the patient's routine clinical care will generate the randomization list.

Envelope containing computer generated randomized allocations will be given to the research team. Randomization envelopes will only be open 30 minutes prior to the procedure. To maintain the proper concealed allocation the research team will maintain a randomization sheet with randomization number, subject initials, time and date of the procedure.

As all data is to remain anonymous and to be reported in aggregate (any value less than 1% will be aggregated with the most similar group (including diagnosis and age), we anticipate minimal physical, psychological risks to individual patients.

Data will remain de-identified and no personal identifiers will be queried unless an outlier is found. Subsequent to review by the research team any outliers that cannot be excluded will receive a chart review. For chart review the IRB code will be kept in the desk of and used exclusively by the principle investigator.

Following identification by the principal investigator, charts of outliers may be

reviewed for verification of number of opiate prescriptions. This data will be reconfirmed in the anonymized database/spreadsheet.

STATISTICAL ANALYSIS

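### The plan names a log kept by the research team as its means of concealment, and no stated rule completes consent and eligibility, or ties a number to a patient, before the envelope is opened

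*Combined protocol and SAP*

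**What the plan says.** All references are to the combined protocol and SAP.

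- **List (RANDOMIZATION).** "Anesthesia research office that is not part of the patient's routine clinical care will generate the randomization list". No later role for that office is described.
- **Custody (RANDOMIZATION).** "Envelope containing computer generated randomized allocations will be given to the research team".
- **Timing (RANDOMIZATION).** "Randomization envelopes will only be open 30 minutes prior to the procedure".
- **Stated means of concealment (RANDOMIZATION).** "To maintain the proper concealed allocation the research team will maintain a randomization sheet". The fields of the sheet are number, initials, time and date. The assigned arm is not among them.
- **Consent (STUDY POPULATION).** "The patients will be consented by a member of the study team". On timing: "On the day of the procedure or if possible prior to the procedure the patient will sign written consent".
- **Group sizes (STUDY DESIGN).** "Eligible patients will be randomized into two groups of thirty patients each". Neither the type of randomization nor any block size is given.
- **Exclusions (STUDY DESIGN).** A patient is excluded if the assigned anesthesiologist is unfamiliar or uncomfortable with HFNC, and intubated patients are excluded. Neither exclusion is placed before or after envelope opening.

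The text does not say whether the envelopes are sealed, opaque or sequentially numbered.

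**The concern.** Concealment means that whoever decides on a patient's entry cannot know or predict that patient's allocation until entry is irrevocable. A sheet of numbers, initials and times helps to detect irregularities afterwards, but it does not provide this. Here the envelopes, the sheet and consent appear to sit with one group, and the point at which a patient becomes committed to a number is not defined.

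Two routes to bias follow. In the first, someone who can predict the next allocation influences which patient takes it. In the second, the envelope is opened and a discretionary exclusion is then applied, for example the anesthesiologist's discomfort with HFNC after an HFNC allocation has been seen. The second route needs no guessing and exists even under simple randomization. The intention-to-treat statement in the Analysis plan would not restore patients removed from the study in this way.

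The setting makes either route matter. HFNC at 50 lpm and a cannula at 5 lpm cannot be mistaken for each other, and no blinding is described. The primary outcome depends on airway maneuvers, which are partly a matter of clinician judgment. The Sample size calculation section shows that the investigators already expect fewer of them with HFNC. Selection bias of this kind cannot be reliably repaired in analysis.

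**Working it through.** **Plan's own figure.** The plan gives no figure for concealment. Its 25 per group reproduces with the pooled two-sided formula for 90% versus 55%: [1.960·√(2·0.725·0.275) + 0.842·√(0.9·0.1 + 0.55·0.45)]² / 0.35² = 24.3, rounded up to 25. Nothing below depends on it.

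**Step 1: what each stated element does.**

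| Element | Effect on concealment |
|---|---|
| Separate office makes the list | Keeps generation away from routine care; silent on custody |
| Envelopes opened 30 minutes before | Delays disclosure; does not say consent and eligibility must be complete |
| Sheet kept by the research team | Audit trail only; not stated to be filled in before opening |
| Consent by a study team member | Puts consent beside custody, if the two team names mean the same people |

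**Step 2: how predictable the next assignment could be.** Assume that all earlier assignments are known from the visible devices, and that the guess is always the arm with more places left (a coin toss when equal). For permuted blocks of size 2m:

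- Share of correct guesses = [m + (4^m / C(2m, m) − 1)/2] / (2m).
- Share of assignments known with certainty = 1/(m + 1).

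Blocks of 4 (m = 2): [2 + (16/6 − 1)/2]/4 = 0.708, and 1/3. Blocks of 6 (m = 3): [3 + (64/20 − 1)/2]/6 = 0.683, and 1/4. One list of 60 (m = 30): 0.573, and 1/31 = 0.032.

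| List (assumed) | Correct guesses | Certain |
|---|---|---|
| Simple randomization | 50.0% | 0% |
| One 30/30 list | 57.3% | 3.2% |
| Blocks of 6 | 68.3% | 25.0% |
| Blocks of 4 | 70.8% | 33.3% |

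**Step 3: what it could do to the test.** The simulation has 60 patients, the planned chi-square test at two-sided 0.05, and no HFNC effect. Half the available patients are assumed to have a 95% chance of the outcome and half 65%. When the guess is cannula a higher-risk patient is entered, and when it is HFNC a lower-risk one. The expected false difference is (2 × share correct − 1) × 0.30. For blocks of 4 that is 0.417 × 0.30 = 12.5 points, for blocks of 6 it is 11.0 points, and for one list it is 4.4 points.

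| Assumption | Blocks of 4 | Blocks of 6 | One 30/30 list |
|---|---|---|---|
| Every informative guess acted on | 22% | 17% | 6–7% |
| Half of the guesses acted on | 9% | 8–9% | 5–6% |
| A quarter acted on | 5–6% | 5–6% | 5–6% |
| Full steering, risks 95%/85% | 9% | 8% | 5–6% |
| Full steering, 95%/65%, last two assignments unknown | 5–7% | 5–7% | 5–7% |

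Entries are type I error rates. Under simple randomization the rate stays at about 5%. With 6,000 trials per setting, the simulation standard error is about 0.3 to 0.5 points. Block size, risk split, steering share and lag are all assumptions, because the documents give none of them.

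**The case against.** The strongest reply is that this is thin description rather than proven failure, and much of it stands. A reader might infer several things that the documents do not support:

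- **That concealment rests on the log alone.** It does not. The outside office, the envelopes and the delayed opening are real, if partial, protections.
- **That the team which consents also screens and telephones.** The STUDY POPULATION section leaves those steps in the passive voice and places chart review within the usual anesthesia assessment. Only consent is assigned. Even there, the text says study team for consent and research team for the envelopes, and does not say that they are the same people.
- **That the sheet reveals the sequence.** The arm is not a listed field. Any knowledge of past assignments would come from the visible devices or the opened envelopes.
- **That the list is blocked.** Thirty per group suggests a restricted list but may only be a target. Under simple randomization guessing gains nothing.
- **That type I error will be 17% to 22%.** That needs small blocks, full knowledge of past assignments, action on every informative guess, patients of both risk types always at hand, and a 95%/65% split. The split averages 80%, whereas the plan expects 90% on the standard cannula. Patients are identified a few days ahead on an elective schedule, so earlier envelopes may still be unopened.

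What the reply does not remove is that the plan names an audit trail as its means of concealment and defines no point at which a patient is committed. It can also fairly be said that a sentence on sealed, numbered envelopes and prior entry on the sheet would close much of the gap. That is the minimum offered below.

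**Conclusion.** The point holds in limited form. Adequate concealment cannot be verified from the text, and the means it names does not conceal. The main weakness is order. Nothing stated requires written consent, final eligibility and assignment of a number to a patient to come before opening, while two exclusions remain untimed. In a visibly open trial with an outcome that depends on judgment, this leaves room for selection and for exclusion after allocation.

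The size is uncertain. If the list is restricted, the next assignment could be guessed about 57% (one 30/30 list) to 71% (blocks of 4) of the time, against 50% under simple randomization. Type I error could be anywhere from the nominal 5% to about 22%, and the upper end is an extreme case rather than an expectation. Bias through exclusion after opening is not quantified, because the documents give no basis for a rate. The change is worth making before enrollment because a less bias-prone arrangement is available at small cost from an office already in the plan.

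**What to change.** Revise the RANDOMIZATION section as follows.

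1. The anesthesia research office keeps the list and the sealed, opaque, sequentially numbered envelopes.
2. Before release, written consent is signed and all eligibility checks are complete, including the assigned anesthesiologist's agreement to use HFNC. The patient is entered against the next number with date and time.
3. The office then releases the allocation 30 minutes before the procedure. From entry onward the patient belongs to the randomized set.
4. The office reconciles the log with the master list at the end and reports any number used out of order.
5. The randomization type is stated. The list uses one large block or varied block sizes not disclosed to the team.
6. The sheet is described as an audit record and no longer as the means of concealment.

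The cost is one contact per patient and no extra patients. The office must be reachable shortly before each procedure, and the documents do not say whether it is. If it cannot be, the minimum is for the team to enter each patient on the existing sheet against the next sealed, numbered envelope before opening it.

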Sample size calculation

Primary objective of this study is to evaluate the effects of HFNC on maintaining ventilation and oxygenation in the two groups. For the purpose of this study if a patient is getting 5 or more air way manipulations such as chin lift and jaw thrust or any other direct interventions to maintain the ventilation and oxygenation will be categorized into the group need for additional support to maintain ventilation and oxygenation. According to our clinical audit when using the standard of care nasal cannula 90% of the patients required additional support for maintaining ventilation and oxygenation. HFNC is now been routinely used in our ORs. We have observed that in majority of the patients when HFNC was used the need for additional airway manipulations were minimal when compared to the regular oxygen cannula. For the purpose of this pilot study sample size calculations are based on the assumptions that 90% of patients using regular cannula will require additional airway manipulations while only 55% in the HFNC group requires the same. Based on a two-sided alpha of 0.05 and Type II error of 20% to achieve a statistically

significant difference between the two groups we need to study 25 patients in each group, a total of 50 patients. Additionally, we plan to increase our sample size by 10% to accommodate for attritions.

Analysis plan

All the analysis will be intention-to-treat analysis. Standard descriptive statistics will be used to explain demographic and clinical characteristics (age, gender, type of surgery, pre-entry medications, ASA status, surgeon, co-morbidities, etc.). The analysis plan assumes that the primary outcome of the trial the proportion of patients requiring addition airway support will be analyzed using the chi-square analysis. Percentage of patients requiring FiO₂ will also be analyzed using chi-square analysis. For all continuous monitoring measurements such as TcCO₂ and TcO₂ the measurements will be averaged for first 5 minutes before the start of any procedure activities and this measurement will serve as the baseline measurement. For all subsequent measurements every 15 minute measurements will be averaged and a delta value will be created comparing it to the baseline. The delta value created will be compared between the two groups.

CONCLUSION:

In the past decade, the obesity epidemic has resulted in a growing need for novel approaches to improve patient safety when receiving anesthesia. First shown

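### The only outlier rule gives no criterion, can be read as allowing exclusion before any source check, and verifies a variable that is not part of this trial

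*Combined protocol and SAP*

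**What the plan says.** The relevant text is in the data-handling paragraphs that follow the envelope procedure under RANDOMIZATION. They open with anonymity and aggregate reporting, then state: "Data will remain de-identified and no personal identifiers will be queried unless an outlier is found". The next sentence is the only one on what happens to outliers: "Subsequent to review by the research team any outliers that cannot be excluded will receive a chart review". On access: "For chart review the IRB code will be kept in the desk of and used exclusively by the principle investigator". The charts of outliers may then be "reviewed for verification of number of opiate prescriptions", and the result is reconfirmed in the anonymized database.

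On allocation, the same section says "Envelope containing computer generated randomized allocations will be given to the research team" and that "the research team will maintain a randomization sheet with randomization number, subject initials, time and date of the procedure".

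Under OUTCOMES: "Secondary endpoints will include the lowest and mean pulse oximetry readings", together with transcutaneous CO₂ and O₂ (TcCO₂, TcO₂) and their changes over the procedure. The Analysis plan states: "All the analysis will be intention-to-treat analysis". It has no step for outliers, extreme values or missing values.

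**The concern.** Three features combine.

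- **Order of steps.** The team's review comes first, and only outliers that survive it reach a chart. No variable, threshold, ground for exclusion or record of exclusions is given.
- **Content of the check.** A count of opiate prescriptions says nothing about whether a low saturation, a high TcCO₂ or a recorded airway maneuver was real.
- **Possible knowledge of arm.** The team that reviews outliers also receives the envelopes.

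In most datasets an outlier is a nuisance. Here a nadir saturation is an extreme by definition, and a large rise in TcCO₂ is the hypoventilation signal that the trial sets out to measure. Discretion over extremes is therefore discretion over the result for those endpoints.

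**Working it through.** **1. Passages side by side**

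| Question | What the document gives |
|---|---|
| What counts as an outlier? | No variable, threshold or method |
| Who reviews first? | The research team |
| On what ground may one be excluded? | None stated |
| Which outliers reach a chart? | Only those that cannot be excluded |
| Is that chart review certain? | One sentence says it will happen, a later one that charts may be reviewed |
| What does it verify? | Number of opiate prescriptions |
| Is that an endpoint or named variable? | No; absent from OUTCOMES, STUDY DESIGN and the Analysis plan |
| Are exclusions logged, or analyses run both ways? | Not mentioned |
| Is the team, an assessor or an analyst masked? | Not described |

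**2. The plan's own figure.** The sample size is not in question. With 90% and 55%, two-sided alpha 0.05 and 80% power, the mean proportion is 0.725, and

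n = [1.960·√(2·0.725·0.275) + 0.842·√(0.90·0.10 + 0.55·0.45)]² / 0.35² = 24.3, so 25 per group, as stated.

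The illustrations below use the 30 per group in STUDY DESIGN.

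**3. Continuous secondary endpoints: an assumed example.** The documents give no means or SDs. Suppose that in one arm 28 patients have saturation nadirs with mean 94% and SD 2.5, and two patients fall to 75%.

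- Mean of all 30: (28·94 + 2·75)/30 = 92.73.
- SD of all 30: √{[27·2.5² + 28·(94 − 92.73)² + 2·(75 − 92.73)²]/29} = 5.39.
- With roughly normal values, the quartiles are 91.94 and 95.48. The usual boxplot fence is 91.94 − 1.5·(95.48 − 91.94) = 86.6, so both low values would be flagged. The plan names no fence; this is one common choice.
- Without the two patients: mean 94.0, SD 2.5. The mean moves by 1.27 points and the SD more than halves.
- Two such patients in 30 is 6.7% (exact 95% CI 0.8% to 22.1%); after removal the arm shows none.

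**4. Effect on type I error (simulation).** Assumptions: normal data, equal SDs, no true difference, 30 per arm, two-sided t-test at 5%. The plan names no test for the change values.

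| Values removed on one side | Shift in arm mean (SD units) | Removed from one arm only | Same number removed from both arms |
|---|---|---|---|
| 0 | 0 | 5.0% | 5.0% |
| 1 | 0.07 | 6.5% | 6.3% |
| 2 | 0.13 | 9.0% | 7.3% |
| 3 | 0.19 | 12.6% | 8.1% |

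The last column shows that even-handed removal also raises the error, because it shrinks the estimated SD. Removal from one arm does more harm.

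**5. Primary outcome.** It is dichotomized at five or more manipulations, so a very large count is simply one event and has no extra leverage. It moves only if a whole patient is dropped. A deliberately borderline example, by chi-square without continuity correction: 27/30 against 21/30 gives p = 0.053. Dropping one HFNC patient with an event gives 27/30 against 20/29, p = 0.045. With continuity correction the values are 0.107 and 0.092, so neither reaches 5%.

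**The case against.** The strongest reply is that this is not an analysis rule. The paragraph deals with confidentiality and with when identifiers may be unlocked. On that reading, an outlier that cannot be excluded is one that cannot be ruled out as an error, and nothing says that the others leave the dataset. The opiate reference suggests text carried over from another study. This reading is reasonable. It still leaves a first decision made without source, a check that does not fit the trial, and no other rule for extreme values.

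Some stronger inferences are tempting but are not supported:

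- **That the research team is unblinded.** The documents do not say so. They do not say who opens the envelopes, and the listed contents of the randomization sheet do not include the arm. What stands is that the team receives the envelopes and no masking is described. De-identification hides identity, not treatment.
- **That the rule contradicts intention-to-treat.** Setting aside one reading does not. Removing a randomized patient would, and the text does not say which is meant. The intention-to-treat statement may be read as barring patient exclusion, but it sets no rule for individual readings.
- **That a severe-event rate would be erased.** No severe-desaturation rate is among the endpoints; the plan names the lowest and mean readings.

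It can also be said that prior opioid use might fall under the pre-entry medications listed among the baseline characteristics. Even so, a prescription count is not named and could not verify an airway or gas-exchange value.

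**Conclusion.** The concern holds in a limited form. The only outlier rule in the document has no criterion, can be read as permitting exclusion before any source check, and directs the remaining check at something outside the trial. That leaves avoidable discretion over the lowest and mean saturation, TcCO₂ and TcO₂, possibly with the arm known. The primary outcome is exposed only through removal of whole patients.

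The size cannot be derived from the documents. Under the stated assumptions, selective removal of one to three values from one arm of 30 raises a nominal 5% error to about 6.5% to 12.6%. These figures show what the wording would allow, not what the investigators intend or what will happen. Because the harm depends on one reading of misplaced text and falls mainly on secondary endpoints of a pilot, the point should be corrected but ranks below a must-fix.

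**What to change.** Delete the outlier and opiate-prescription sentences under RANDOMIZATION and put a short rule in the Analysis plan:

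1. No randomized patient and no physiologically possible value is excluded for being extreme.
2. A reading is set aside only for documented sensor artefact or data-entry error, checked against the anesthesia or recovery record by someone masked to arm.
3. Every removal is logged with its reason and tabulated by arm.
4. Affected secondary endpoints are reported with and without the removed readings.

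The anesthesia research office could supply the masked reviewer. Because that office generates the randomization list, the reviewer should have no access to the list and should work from an extract that does not show the oxygen device.

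The cost is protocol wording, a few more records checked and the preparation of masked extracts. The downside is that a few artefacts may stay in the main analysis. Sample size, treatment and procedures do not change.

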¹². The experimental group will receive oxygen via HFNC at 50 lpm and FiO₂ of 0.35 for the procedure. The control group will receive oxygen via nasal cannula at 5lpm (approximately an FiO₂ of 0.35) for the procedure. Each participant will receive monitored anesthesia care (MAC) with moderate sedation with Propofol.

A loading dose of 1 mcg/kg ideal body weight followed by an infusion starting at 125 mcg/kg/min and titrated to desired level of sedation. At the discretion of the Anesthesiologist the patient may receive 50 to 100mcg of Fentanyl IV PRN. All patients will be monitored using standard American Society of Anesthesiologists monitors, which include continuous EKG, heart rate, pulse oximetry, and non-invasive blood pressure monitoring. Monitoring end tidal carbon dioxide (ETCO₂) to insure adequate ventilation by capnography during moderate sedation can be problematic, due to movement of the cannula or patient preference for mouth breathing preventing adequate uptake of expired gas for analysis. In addition, the high flow rates of the HFNC prevent the measurement of ETCO₂. Ventilation will be monitored in both groups by observing chest movement and by ECG derived respiratory signals¹³. In addition, transcutaneous CO₂ (TcCO₂) and O₂ (TcO₂) levels will be monitored throughout the procedure.

Airway maneuvers required to aid in ventilation or oxygenation during the sedation portion of the procedure will be recorded and are classified as chin lift maneuver, airway insertion, increased FiO₂, active ventilation, and lastly aborting of procedure or intubation. Chin lift maneuver is characterized by lifting of the chin or jaw-thrust maneuver in order to improve ventilation and/or oxygenation. Insertion of an oral or nasal airway helps insure patency of the airway by preventing obstruction by the tongue. Increased FiO₂ will be achieved by

placement of face-mask over the patient's mouth and nose, airway patency can be helped by applying a low level of positive pressure. If oxygenation and/or ventilation continues to be problematic active ventilation can will be performed. The last classification is for any procedure that is aborted early due to respiratory complications or if the patient requires general anesthesia and intubation in order to insure proper ventilation/ oxygenation.

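### The number of airway maneuvers is analyzed only as a yes/no outcome expected to be 90% positive in controls; against a rank test on the count, this gives up about a third to a half of the power at 20 to 25 points

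*Combined protocol and SAP*

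**What the plan says.** **What is recorded.** Study Design has airway maneuvers recorded in five classes: chin lift or jaw thrust, airway insertion, increased FiO2, active ventilation, and abort or intubation. On the fifth it says: "The last classification is for any procedure that is aborted early due to respiratory complications", and it adds conversion to general anesthesia with intubation.

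**How it becomes an outcome.** Under Sample size calculation, a patient counts as needing support "if a patient is getting 5 or more air way manipulations such as chin lift and jaw thrust or any other direct interventions" to maintain ventilation and oxygenation. The control rate comes from local experience: "According to our clinical audit when using the standard of care nasal cannula 90% of the patients required additional support". The design assumption is that "90% of patients using regular cannula will require additional airway manipulations while only 55% in the HFNC group requires the same", and the conclusion is that "we need to study 25 patients in each group, a total of 50 patients". Study Design randomizes thirty per group.

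**How it is analyzed.** Under Analysis plan, "the proportion of patients requiring addition airway support will be analyzed using the chi-square analysis". That section also plans a chi-square on the percentage needing FiO2 and a comparison of changes in TcCO2 and TcO2 from baseline. Outcomes lists interruption or aborting of the procedure as an additional endpoint. No analysis uses the number of maneuvers beyond the cut, or the order of the classes.

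**The concern.** The hypothesis in the Background is that HFNC reduces the need for airway manipulation, which is a matter of degree. On the count reading of the rule, a patient with 5 chin lifts and one with 20 score the same, and a fall from 15 manipulations to 6 scores as no benefit. With 90% of controls expected above the cut, HFNC registers an effect only by bringing patients below five.

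The 35-point effect rests on an unquantified observation that few manipulations were needed with HFNC. If the true effect is nearer 20 points, the trial is more likely than not to find no significant difference, although the recorded counts might show one. For a pilot, graded information is a large part of what the study can contribute to planning.

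**Working it through.** **1. Inputs from the documents.** Two-sided alpha 0.05 (z = 1.960), power 80% (z = 0.842), rates 0.90 and 0.55, 25 evaluable and 30 randomized per arm, cut at five.

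**2. The plan's own figure.** With the pooled-variance formula and no continuity correction,

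n = [z_α √(2 p̄ q̄) + z_β √(p1 q1 + p2 q2)]² / (p1 − p2)²

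- p̄ = 0.725, so √(2 × 0.725 × 0.275) = 0.6315.
- √(0.09 + 0.2475) = 0.5809.
- n = (1.960 × 0.6315 + 0.842 × 0.5809)² / 0.35² = 2.98 / 0.1225 = 24.3, rounded up to 25.

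The stated 25 per arm reproduces exactly.

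**3. Planned chi-square at smaller effects.** Power = Φ{[(p1 − p2)√n − z_α √(2 p̄ q̄)] / √(p1 q1 + p2 q2)}. For 90% versus 70% with n = 25: (0.20 × 5 − 1.960 × 0.5657) / 0.5477 = −0.199, so power is 42%. The same formula for n shows that 80% power at this effect needs 62 per arm.

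**4. Rank test on the uncut count.** The documents give no count distribution, so this step is an assumption. Counts were simulated as Poisson or as negative binomial with variance m + m²/k. They were calibrated so that P(5 or more) is 90% in controls and equals the stated rate in HFNC. At 90% versus 70% the means are 8.0 and 5.9 (Poisson), or 19.6 and 9.0 (k = 2). There were 6,000 trials per setting. Power (%) is shown as 25 / 30 per arm, and the ranges run from Poisson to k = 2:

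| HFNC rate (control 90%) | Chi-square, formula | Chi-square, simulated | Wilcoxon on count |
|---|---|---|---|
| 55% | 81 / 88 | 83-84 / 89-90 | 98-99.6 / 99-100 |
| 65% | 57 / 65 | 60-61 / 65-66 | 89-96 / 94-99 |
| 70% | 42 / 49 | 44-45 / 49-51 | 77-88 / 84-94 |
| 75% | 28 / 33 | 29-31 / 33-34 | 58-74 / 67-83 |
| 80% | 16 / 19 | 17-18 / 18-20 | 35-49 / 40-58 |

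With equal arms the Wilcoxon test rejected in about 4.4-5.1% of trials. Under Poisson it needs roughly 25-30 per arm for 80% power at 90% versus 70%, against 62 for the chi-square. Across repeated simulations, the comparison at 90% versus 70% with 25 per arm spans about 42-46% against 75-90%.

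**5. Share of power given up, 25 per arm, simulated values (Poisson; k = 2).**

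- 25 points: 1 − 0.600/0.888 = 32%; 1 − 0.602/0.961 = 37%.
- 20 points: 1 − 0.442/0.769 = 43%; 1 − 0.446/0.880 = 49%.
- 15 points: 1 − 0.298/0.579 = 49%; 1 − 0.294/0.743 = 60%.

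Using the formula values 57% and 42% instead gives 36-41% at 25 points and 45-52% at 20 points.

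**6. Does the gain survive a workable ranking?** Aborted or intubated cases have truncated counts, so a plain count could make a bad outcome look good. Two rankings were simulated at 90% versus 70% with 25 per arm, against 42-46% for the chi-square:

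- *Abort or intubation worst, everyone else by count.* If such cases are equally common in both arms and unrelated to the count, power is about 69-84% when they are 3% of each arm and about 55-71% when they are 10%.
- *Worst class first, count only to break ties.* If 30% of each arm reach a class above chin lift regardless of treatment, power is 26-34%, below the chi-square. If HFNC does shift the class, an ordinal model of highest class reached gives 58-72%. The documents give no class distribution to choose between these cases.

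**The case against.** The strongest reply is that nothing here is an error. The sample size is right for its assumptions, a binary primary is coherent, the trial is labeled a pilot, and a secondary analysis leaves the power of the primary where it was. All of that stands. It limits the point to a supportive addition and gives no reason to replace the primary.

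The outcome rule is also ambiguous. The clause on other direct interventions may mean that one such intervention is enough, and the plan does not say that the audit's 90% used the five-or-more rule. On that reading the calibration in step 4 is less secure. The outcome would still be binary with 90% of controls positive, and would still ignore number and severity.

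Three stronger readings are tempting, and none is supported:

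- *The chi-square is the only planned analysis.* It is the only one of the number of maneuvers. Analysis plan also covers FiO2, itself one of the recorded classes, and TcCO2/TcO2 changes; Outcomes lists aborted procedures.
- *The cut discards most of the power for any effect below 35 points.* The loss is about a third at 25 points and 40-50% at 20; it clearly exceeds half only at about 15 points or less.
- *Ranking patients by severity class would recover the power.* Step 6 shows that this ranking can do worse than the planned test. The documents also do not state that each listed class is worse than the one before; they single out only the last.

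**Conclusion.** The point holds as a moderate one. Maneuvers are recorded, and their number is then reduced to a single cut near a 90% ceiling. Compared with a rank test on the count, that costs roughly a third of the power at 25 points and 40-50% at 20 points. The size depends on the assumed Poisson to negative binomial (k = 2) counts and on reading the rule as a cut at five. The direction was the same in every count distribution tried. The stated 25 per arm is not in question.

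**What to change.** Keep the binary chi-square as the primary analysis and add to the SAP:

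1. One supportive secondary analysis: a two-sided Wilcoxon rank-sum test on the per-patient number of manipulations. Procedures aborted for respiratory reasons or converted to intubation share the worst rank. Report the probability that an HFNC patient fares better than a control patient (ties counted as one half), with 95% CI.
2. A descriptive table of worst class reached, by arm. Do not rank by class first.
3. A statement that the full count per patient is captured, not only whether it reached five, and one unambiguous reading of the clause on other direct interventions.
4. A reconciliation within Study Design. One paragraph excludes patients who are intubated, while another makes intubation an outcome class, and Analysis plan calls for intention-to-treat. The context suggests that the exclusion concerns elective intubation before sedation, but the text should say so before intubation can be ranked worst.

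The cost is SAP wording and one extra analysis of data that the protocol already intends to record. The worst-rank rule must be fixed before data are seen, and the result remains supportive.
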